#### 16.6 PROTOCOL MODIFICATIONS AND DEVIATIONS

The PI will submit Protocol modifications to the IRB as necessary.

## 18. APPENDICES

### 18.1 APPENDIX 1: BMI RANGES TARGETED FOR MEN AND WOMEN ENROLLED IN STUDY 15,16

Males (target BMI indicated by Black Bars):

WEIGHT Ibs 100 105 110 115 120 125 130 135 140 145 150 155 160 165 170 175 180 185 190 195 200 205 210 215 45.5 47.7 50.0 52.3 54.5 56.8 59.1 61.4 63.6 65.9 68.2 70.5 72.7 75.0 77.3 79.5 81.8 84.1 86.4 88.6 90.9 93.2 95.5 97.7 HEIGHT in/cm Extremely obese Underweight Healthy Obese Overweight 5'0" - 152.4 20 21 22 5'1" - 154.9 5'2" - 157.4 5'3" - 160.0 5'4" - 162.5 5'5" - 165.1 5'6" - 167.6 5'7" - 170.1 5'8" - 172.7 5'9" - 175.2 5'10" - 177.8 14 15 5'11" - 180.3 6'0" - 182.8 6'1" - 185.4 6'2" - 187.9 6'3" - 190.5 19 20 6'4" - 193.0 14 14 15 15 16 17 18 18

### Females (target BMI indicated by Black Bars):

WEIGHT lbs 100 105 110 115 120 125 130 135 140 145 150 155 160 165 170 175 180 185 190 195 200 205 210 215 kgs 45.5 47.7 50.0 52.3 54.5 56.8 59.1 61.4 63.6 65.9 68.2 70.5 72.7 75.0 77.3 79.5 81.8 84.1 86.4 88.6 90.9 93.2 95.5 97.7

HEIGHT in/cm		Und	erweig	ght			Hea	lthy				Ove	rweig	ht			Obe	se			Extr	emely	obes	e
5'0" - 152.4	19	20	21	22	23	24	25	26	27	28	29	30	31	32	33	34	35	36	37	38	39	40	41	42
5'1" - 154.9	18	19	20	21	22	23	24	25	26	27	28	29	30	31	32	33	34	35	36	36	37	38	39	40
5'2" - 157.4	18	19	20	21	22	22	23	24	25	26	27	28	29	30	31	32	33	33	34	35	36	37	38	39
5'3" - 160.0	17	18	19	20	21	22	23	24	24	25	26	27	28	29	30	31	32	32	33	34	35	36	37	38
5'4" - 162.5	17	18	18	19	20	21	22	23	24	24	25	26	27	28	29	30	31	31	32	33	34	35	36	37
5'5" - 165.1	16	17	18	19	20	20	21	22	23	24	25	25	26	27	28	29	30	30	31	32	33	34	35	35
5'6" - 167.6	16	17	17	18	19	20	21	21	22	23	24	25	25	26	27	28	29	29	30	31	32	33	34	34
5'7" - 170.1	15	16	17	18	18	19	20	21	22	22	23	24	25	25	26	27	28	29	29	30	31	32	33	33
5'8" - 172.7	15	16	16	17	18	19	19	20	21	22	22	23	24	25	25	26	27	28	28	29	30	31	32	32
5'9" - 175.2	14	15	16	17	17	18	19	20	20	21	22	22	23	24	25	25	26	27	28	28	29	30	31	31
5'10" - 177.8	14	15	15	16	17	18	18	19	20	20	21	22	23	23	24	25	25	26	27	28	28	29	30	30
5'11" - 180.3	14	14	15	16	16	17	18	18	19	20	21	21	22	23	23	24	25	25	26	27	28	28	29	30
6'0" - 182.8	13	14	14	15	16	17	17	18	19	19	20	21	21	22	23	23	24	25	25	26	27	27	28	29
6'1" - 185.4	13	13	14	15	15	16	17	17	18	19	19	20	21	21	22	23	23	24	25	25	26	27	27	28
6'2" - 187.9	12	13	14	14	15	16	16	17	18	18	19	19	20	21	21	22	23	23	24	25	25	26	27	27
6'3" - 190.5	12	13	13	14	15	15	16	16	17	18	18	19	20	20	21	21	22	23	23	24	25	25	26	26
6'4" - 193.0	12	12	13	14	14	15	15	16	17	17	18	18	19	20	20	21	22	22	23	23	24	25	25	26

### 18.2 APPENDIX 2: TENS UNIT USER MANUALS (ADDITIONAL FILE SUBMITTED SEPARATELY)

### 18.3 APPENDIX 3: PHQ-9 QUESTIONNAIRE

# PATIENT HEALTH QUESTIONNAIRE-9 (PHQ-9)

Over the last 2 weeks , how often have you been bothered by any of the following problems? (Use 'indicate your answer)	'✔' to Not at all	Several days	More than half the days	Nearly every day		
1. Little interest or pleasure in doing things	0	1	2	3		
2. Feeling down, depressed, or hopeless	0	1	2	3		
3. Trouble falling or staying asleep, or sleeping too mu	uch 0	1	2	3		
4. Feeling tired or having little energy	0	1	2	3		
5. Poor appetite or overeating	0	1	2	3		
6. Feeling bad about yourself — or that you are a failu have let yourself or your family down	re or 0	1	2	3		
7. Trouble concentrating on things, such as reading the newspaper or watching television	e 0	1	2	3		
B. Moving or speaking so slowly that other people cou have noticed? Or the opposite — being so fidgety or restless that you have been moving around a lot more usual	0	1	2	3		

Thoughts that you would be better off dead or of hur yourself in some way

	rting 0	1	2	3		
FOR OF	FICE CODING 0 +	+	+	•		
		=	Total Score	:		
If you checked off any problems, how difficult hav work, take care of things at home, or get along wit		made it fo	r you to do	your		
Not difficult Somewhat	Very		Extrem			
atall difficult □	difficult □		difficult ¯ □			

 $\label{eq:produce} \textbf{Pfizer Inc.} \ \ \textbf{No permission required to reproduce, translate, display or distribute.}$ 

### 18.4 APPENDIX 4: TFEQ-R18V2 17

### The Three-Factor Eating Questionnaire

Please read each statement and select from the multiple-choice options the answer that indicates the frequency with which you find yourself feeling or experiencing what is being described in the statements below.

1. When I smell a delicious food, I find it very difficult to keep from eating, even if I have just finished a meal.

```
Definitely true (4) / mostly true (3) / mostly false (2) / definitely false (1)
```

2. I deliberately take small helpings as a means of controlling my weight.

```
Definitely true (4) / mostly true (3) / mostly false (2) / definitely false (1)
```

3. When I feel anxious, I find myself eating.

```
Definitely true (4) / mostly true (3) / mostly false (2) / definitely false (1)
```

4. Sometimes when I start eating, I just can't seem to stop.

```
Definitely true (4) / mostly true (3) / mostly false (2) / definitely false (1)
```

5. Being with someone who is eating often makes me hungry enough to eat also.

```
Definitely true (4) / mostly true (3) / mostly false (2) / definitely false (1)
```

6. When I feel blue, I often overeat.

```
Definitely true (4) / mostly true (3) / mostly false (2) / definitely false (1)
```

7. When I see a real delicacy, I often get so hungry that I have to eat right away.

```
Definitely true (4) / mostly true (3) / mostly false (2) / definitely false (1)
```

8. I get so hungry that my stomach often seems like a bottomless pit.

```
Definitely true (4) / mostly true (3) / mostly false (2) / definitely false (1)
```

9. I am always hungry so it is hard for me to stop eating before I finish the food on my plate.

```
Definitely true (4) / mostly true (3) / mostly false (2) / definitely false (1)
```

10. When I feel lonely, I console myself by eating.

```
Definitely true (4) / mostly true (3) / mostly false (2) / definitely false (1)
```

11. I consciously hold back at meals in order not to weight gain.

```
Definitely true (4) / mostly true (3) / mostly false (2) / definitely false (1)
```

12. I do not eat some foods because they make me fat.

Definitely true (4) / mostly true (3) / mostly false (2) / definitely false (1)

13. I am always hungry enough to eat at any time.

```
Definitely true (4) / mostly true (3) / mostly false (2) / definitely false (1)
```

14. How often do you feel hungry?

```
Only at meal times (1) / sometimes between meals (2) / often between meals (3) / almost always (4)
```

15. How frequently do you avoid "stocking up" on tempting foods?

```
Almost never (1) / seldom (2) / moderately likely (3) / almost always (4)
```

16. How likely are you to consciously eat less than you want?

```
Unlikely (1) / slightly likely (2) / moderately likely (3) / very likely (4)
```

17. Do you go on eating binges though you are not hungry?

```
Never (1) / rarely (2) / sometimes (3) / at least once a week (4)
```

18. On a scale of 1 to 8, where 1 means no restraint in eating (eating whatever you want, whenever you want it) and 8 means total restraint (constantly limiting food intake and never "giving in"), what number would you give yourself?

Revised 18-Item (Karlsson et. Al. 2000)

# 18.5 APPENDIX 5: VAS AND DAILY DIARY APPLICATION

# Recommended primary scales for self-reported appetite in healthy adultsa

Scale Question		Anchors					
		Low	High				
Hunger	How hungry are you?	Not at all	Extremely As hungry as I have ever felt				
Fullness	How full are you?	Not at all	Extremely As full as I have ever felt				
Satiety	How satiated are you?	Not all	Extremely				
Desire	How strong is your desire to eat?	Very weak Extremely low	Very strong Extremely high				
Prospective consumption (Quantity)	How much do you think you could (or would want to) eat right now?	Nothing at all	A very large amount				

<sup>aLine scales 100-150 mm (paper) or appropriate length for electronic capture systems are to be used for each of these questions.

**44** | Page E L I R A - 1

E LIRA	petite Assessment Diary Protocol: CD-004	
THERAPEUTICS Subject Initials:	Subject Number:	
Directions: Answer each question abut how you ar	re feeling by drawing a mark (   ) through the horizontal line of each question.	
Please complete prior to mealtime. TIME:	_ DAM DATE:	
Table 1 Please indicate below your level of nausea:	Table 2 How Satisfied do you feel?  I am not hungry at all	I have never been more hungry
None Worst Ever  Please indicate below your level of fullness:	I am How full do you feel?  completely empty	I cannot eat another bite
None Worst Ever  Please indicate below your level of bloating:	How hungry do you feel?  Not full	
None Worst Ever	at all  How much do you think you can eat?  Nothing	Totally full
Please indicate below your level of abdominal pain:	Table 3 Would you like to eat something sweet?	A lot
None Worst Ever	Yes, very much	No, not at all
To be completed by study staff:	Would you like to eat something salty?  Yes, very much	No, not at all
Scoring:	Would you like to eat something savory?	
Table One: 1 2 3 4 Table Two: 1 2 3 4	Yes, very much  Would you like to eat something fatty?	No, not at all
Table Three: 1 2 3 4	Yes, very much	No, not at all

**45** | Page E L I R A - 1

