#### 2.1 JUSTIFICATION FOR STUDY GIVEN RISK/BENEFIT OUTCOME

Up to 35% of adults over the age of 20 in the United States are overweight. Being overweight places individuals at higher risk for a number of what are termed metabolic disorders including diabetes mellitus. This risk association is thought to be the reason for the high health care costs associated with overweight and obesity. While diet and exercise do show efficacy in a substantial subset of subjects, long term weight control is difficult to achieve for the vast majority of overweight individuals. The physiological and psycho-social reasons for this are not well characterized and likely highly complex, but a key component of this challenge is associated with appetite control. The present study seeks to determine if a method of appetite control utilizing T6/T7 dermatome stimulation in obese individuals can be utilized to the broader overweight population. The study utilizes non-invasive TENS stimulation within the range of the energy delivery well known to be safe for at-home use for nerve and muscle pain. Subjects will be informed of all potential side effects related to stimulation prior to enrollment and, throughout the study, subjects will be monitored and allowed to decrease or discontinue stimulus if any such side effects are deemed to be intolerable for participants.

In addition, since appetite and weight loss can be affected by a variety of physiological and psychosocial factors (12,13, 15, 17), the change in appetite will be measured weekly using a validated tool, the Visual Analog Scale (VAS; See Appendix 3) and also assessed at baseline at the end of the study via administration of the Three Factor Eating Questionnaire R-18 V2 (TFEQ-R1V2). Please note that while the VAS was first developed for pain, it has been validated for weight loss/appetite applications (14) while the TFEQ-R18V2 has specifically been validated in weight loss applications (17, 18). The present study is not intended to be a formal validation of the assessment tool's applicability to the population targeted by the present study per se; it is intended simply as an assessment of potential changes in such parameters correlated with delivery of therapy during the study. Thus, the use of the tool as presented is considered scientifically valid.

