#### 5.1 Dosing Schedule

All Treatment Subjects will be trained in rotation of the patch electrodes every 24h such that it is applied to varying locations on the T6/T7 dermatome. Each active therapy subject will receive up to 30 mA sustained current of stimulation (up to 40mA peak) for 30 minutes after each of three meals per day (delivered within 1-hour post prandially). Based on tolerance of the therapy, a subject may decrease his or her dose by dropping one of the 3 post prandial sessions after receiving approval from a clinical coordinator and/or PI. Subjects who do not experience sufficient appetite suppression may add up to three 15-minute pre-prandial rescue sessions delivered within 2 hours before each meal after receiving approval from a clinical coordinator and/or PI. The nominal stimulation dose per day for any subject will thus be 2400 mA (60 minutes at 40 mA) while the maximum dose for any given subject will be 5400 mA (135 minutes at 40 mA).

During the therapy period, Treatment Subjects will undergo initial assessments to ensure they are familiar with the device, the daily electronic diary, weekly paper diary, and the 1200 calorie diet. All subjects (Treatment and Control) will be required to undergo follow-up assessments at least once per every 4 weeks during the study. Up to two additional unscheduled visits per subject will be permitted during the study. PI will oversee any adjustments to treatment dosing or stimulation parameters.

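### The weekly appetite form appears to give its hunger and satisfaction questions the wrong anchors and names no meal, so the VAS appetite scores are less reliable than they could be

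*Combined protocol and SAP*

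**What the plan says.** **Anchors.** Appendix 5 (section 18.5) opens with a table of recommended appetite scales. There the hunger question, "How hungry are you", runs between two hunger anchors and the fullness question between two fullness anchors. The study's own weekly form follows. In its Table 2, as the text reads, "How Satisfied do you feel" goes with a low anchor denying hunger and the high anchor "I have never been more hungry". The fullness question goes with a pair running from empty to unable to eat more. "How hungry do you feel" goes with a pair running from no fullness to complete fullness. The fourth question, on how much could be eaten, has fitting quantity anchors.

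**Timing.** The form's instruction is "Please complete prior to mealtime". It has time and date fields but names no meal. Section 9.8 has all subjects complete the diary weekly from screening to the end of the study. Under section 5.1, treatment subjects receive stimulation "for 30 minutes after each of three meals per day (delivered within 1-hour post prandially". With approval, one of these sessions may be dropped, or up to three 15-minute sessions may be added within the 2 hours before meals if appetite suppression is insufficient.

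**Role of the form.** Section 2.1 says "the change in appetite will be measured weekly using a validated tool, the Visual Analog Scale", and adds the TFEQ-R18V2. Section 6.2 draws appetite endpoint data from both Appendix 4 (TFEQ) and Appendix 5 (VAS). Section 6.1.3 makes percentage change in appetite score a secondary endpoint without naming an instrument. Section 8.1.2 names the TFEQ as the appetite score to be correlated with dose.

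**The concern.** If the form is printed as it reads, two of its four appetite items have no definite direction. A very hungry subject would mark the hunger line near the right end if guided by the question and near the left end if guided by the anchors. On the satisfaction line, the right end means most satisfied by the question and hungriest by the anchors. A real fall in hunger could then be recorded as a rise by some subjects.

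Separately, a weekly rating before an unnamed meal can be a pre-breakfast reading at screening and a pre-dinner reading at week 12. In the treatment arm, the interval since the last session varies with the meal, with any dropped session and with any pre-meal session. Pre-meal sessions exist only in that arm, only after baseline, and are offered to subjects whose response has been weak. The lag therefore depends on both arm and response.

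At stake is the reliability of the VAS scores that feed the secondary appetite endpoint. Weight loss, the primary effectiveness endpoint, is not involved.

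**Working it through.** The documents give no effect size, SD, power or scoring rule for appetite, so there is no figure of the plan's to reproduce. The check reads the form against the reference table, then shows how large the effects could be under stated assumptions.

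**1. Is the mispairing real?** Two features of the text bear on it.
- The text is interleaved: it reads "I am How full do you feel", with the rest of the low anchor (empty) coming after the question. An anchor wrapped around a question suggests that the two share a printed row. That would make the fullness item's anchors as read the printed ones, and the mispairing genuine.
- Moving the hunger question from third to first in Table 2 makes the hunger, satisfaction and fullness pairs all match and leaves the quantity item correct. A single displaced line, in print or in text extraction, would produce what is seen.

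These point in different directions, so only the printed form can settle the matter.

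**2. Effect of reversed reading on one item.** Let d be the true change and q the share of subjects who follow the anchors, the same in both arms and consistent over time (assumed). The expected change is (1-q)d - qd = (1-2q)d.

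Power illustration: 75 per arm (section 8.2) less 30% dropout is 75 × 0.70 = 52.5, taken as 52. Assume a true effect of 0.5 SD and two-sided alpha 0.05. Power = Φ(0.5(1-2q)√(52/2) - 1.96).

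| q | effect (SD) | power |
|---|---|---|
| 0 | 0.50 | 72% |
| 10% | 0.40 | 53% |
| 25% | 0.25 | 25% |
| 50% | 0 | no signal |

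At q = 100% the size is kept and the sign reverses.

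Percentage change can be worse. A fall in hunger from 80 to 60 mm is -20/80 = -25% by the question. By the anchors the same subject moves from 20 to 40 mm, which is +20/20 = +100%. At q = 20% the mean is 0.8 × (-25) + 0.2 × 100 = 0. The scores and q are assumptions.

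**3. Lag from the end of the last session to the form.** Assume 4 to 6 h between daytime meals and 10 to 14 h overnight. A 30-minute session starting within 1 h of the meal ends 0.5 to 1.5 h after it.
- Before a daytime meal: 4 - 1.5 = 2.5 h to 6 - 0.5 = 5.5 h.
- Before breakfast: 10 - 1.5 = 8.5 h to 14 - 0.5 = 13.5 h.
- After an added pre-meal session: 0 h to 2 - 0.25 = 1.75 h.

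A dropped session lengthens the lag by a further meal interval.

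**4. Noise from the unfixed meal.** If it adds variation with SD equal to r times the item SD, the effect in step 2 is divided by √(1 + r²). With q = 0, power falls from 72% to 70% (r = 0.25), 63% (r = 0.5) or 44% (r = 1). The values of r are assumed.

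**The case against.** The strongest objection is that the mismatch may come from text extraction. The form is a multi-column graphic, anchors are visibly split, and one moved line repairs every pair. This stands as a reason to check the print before changing anything. It does not dispose of the point, because the wrapped anchor described above suggests a real misordering.

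On timing, a pre-meal rating is a standardised state asked of both arms, and the form records time and date. Section 5.2 records changes to the session schedule, section 6.2 has subjects trained and assessed on the diary, and section 9.11 has the phone capture hunger daily. Much of this stands: an unfixed meal mainly costs precision, and the recorded times allow a partial description. However, clock time does not identify the meal or the last session, and the phone is given to the treatment arm only, so it cannot supply a between-arm comparison.

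A reader might go further and infer that the form leaves the trial unable to answer its appetite question. The documents do not support that. The TFEQ goes to all subjects at enrollment, each therapy visit and the last visit (section 9.8), is named in section 8.1.2, and has none of these faults. Nor do they support calling the readings troughs and peaks, since no time course of effect is given. Whether the form has lost its validated status also cannot be judged, because section 2.1 relies on a cited source that is not reproduced.

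The TFEQ does not make the form dispensable, though. Section 2.1 assigns weekly appetite change to the VAS, section 6.2 uses both instruments, and many TFEQ items concern restraint or emotional eating rather than current hunger.

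**Conclusion.** The point holds as a cheap improvement to a secondary measure. Two things are clear from the documents: no meal is named, and the time since stimulation is not fixed. A third, the mispairing of the hunger and satisfaction anchors, is how the form reads but is unproven until the printed page is seen.

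If the mispairing is real, the loss on each affected item is the factor (1-2q), and could be anything from negligible to complete depending on how subjects read it. The fullness and quantity items keep a coherent direction even as read. The unfixed meal costs precision, and the pre-meal sessions add an arm-specific difference in lag whose effect on the scores the documents do not allow one to size. All figures rest on the assumed q, r, 0.5 SD effect and meal intervals.

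The VAS scores are therefore less reliable than they need be. How much this matters depends on which score is taken as the appetite endpoint, which section 6.1.3 leaves open.

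**What to change.** 1. Check the printed form. If the mispairing is real, restore matching anchors for hunger, satisfaction and fullness. The wording needed is already on the form.
2. Have every subject in both arms complete the form before the same named meal every week, including the screening week, so that baseline and final readings are alike.
3. Use the form's time field and the session data downloaded at visits (section 9) to describe time since the last session in the treatment arm.
4. Keep all randomised subjects' readings in the main analysis. Excluding readings taken near pre-meal sessions may look like a natural refinement, but it would remove data from one arm only, on the basis of behaviour after randomisation, and mostly from subjects with a weak response. It could flatter the device.

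The cost is one form reprint and one line added to the diary training, with no extra visits. Forms completed before the change would need separate handling, because their anchors, meal or both may differ.

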### 18.6 APPENDIX 6: SCHEDULE OF EVENTS

[figure not shown]
STUDY PERIOD	SCREENING/ BASELINE	ENROLLMENT/ RANDOMIZATION		END OF STUDY 		
VISIT #	VISIT 0	Visit 1	VISIT 2	VISIT 3	VISIT 4	VISIT 5
WEEK#	-1 WEEK	WEEK 0	WEEK 1	WEEK 4	WEEK 8	WEEK 12
VISIT WINDOW 	±7 Days	±7 Days	±7 Days	±7 Days	±7 Days	±7 Days
Informed Consent	Х					
Inclusion/Exclusion Criteria	Х	х				
Medical History	Х					
Diet History	Х					
Physical Exam	Х					Х
T6/T7 dermatome assessment	X 	X 	X 	X 	X 	X 
Blood Pressure	Х	х	х	х	Х	Х
Concomitant Medication Review	Х	х	Х	х	Х	Х
Height	Х					
Weight	Х	х	х	х	Х	Х
Laboratory Requisition - Blood Tests 	Х					Х
Urine Pregnancy Test (WOCBP)	Х	X e				Х
Administration of Patient Preference Survey	Х					Х
Administration of PHQ-9	Х					Х
Administration of TFEQ-R18V2		х	х	х	Х	Х
Provide/Train on Paper Diaries 	Х	х	х	х	Х	
Collect and Review Paper Diaries 		х	х	х	Х	Х
Randomization 		х				
Encourage 1200 calorie diet		х	х	х	Х	
Provide Electronic Scale		х				
Provide and Train on Electronic Diary 		х	х	х	Х	
Collect and Review Electronic Diary 			х	х	Х	Х
Provide and Train on TENS Unit and Patches 		x	x	х	х	
Collect and Examine TENS Unit and Patches 			х	х	х	Х
Provide/Instruct on TENS Clean-Cote Skin Wipes and/or Alcohol Prep Pads 		х	х	х	х	
Provide/Instruct on Cetaphil Lotion 		х	Х	х	Х	
Assessment of Adverse Events	Х	х	Х	х	Х	Х
Assessment of Adverse Device Effects 		х	Х	х	Х	Х
Schedule next visit	Х	х	Х	х	Х	
Study Exit						Х

All visits are ± 7 days
 Blood tests include HbA1c, lipid panel, CMP
 To be completed for control and treatment group

 To be completed for treatment group only 5 – Randomization into control or treatment group

 Complete UPT only if not completed at screening
7 – Complete all procedures at End of Study or Early Termination Visit

